There is increasing evidence that antibody titres to vaccine antigens decrease over time in children who were fully vaccinated prior to chemotherapy.[23-26] A systematic review found that 25-35% of patients who had completed chemotherapy had antibody levels to tetanus and diphtheria that were below protective levels and 70% were susceptible to pertussis.[26] Among 80 children with ALL treated between 2001 and 2010, approximately 30% of those who were seropositive to measles and 17% who were seropositive for varicella at diagnosis subsequently lost immunity to those antigens.[25] In another study of 100 ALL patients who were a mean of 2 years post-chemotherapy, only 42-86% had protective titres to routine childhood vaccines including Hib, hepatitis B, diphtheria and rubella, compared to 96-100% of healthy controls.[23] Seventy-three percent of subjects had non-protective titres to  $\geq 2$  antigens. Studies conducted prior to the introduction of universal infant pneumococcal conjugate vaccination (PCV) reported that pneumococcal antibody concentrations were significantly lower in children with ALL who were 3-6 months post-chemotherapy compared to age-matched healthy controls.[27, 28] No published studies have evaluated the impact of infant PCV immunization on pneumococcal titres post-chemotherapy.

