## **2. Objectives**

- To identify risk factors for low baseline antibody titres to pneumococcal serotypes, tetanus, pertussis toxin, and varicella in previously immunized children diagnosed with ALL at  $\geq 1$  year of age who completed chemotherapy within 6-12 months, as compared to immunocompetent age-matched controls.
- To assess short and long-term immune responses to PCV13 followed by PPV23 in children immunized 6-12 months after completing chemotherapy for ALL.

- To assess short and long-term immune responses to a DTaP-IPV-Hib booster in children immunized 6-12 months after completing chemotherapy for ALL.
- To estimate the frequency of medically-attended AEFI in children immunized after completing treatment for ALL.

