### **6.2 Sample size and Power**

Approximately 278 new cases of ALL are diagnosed annually in Canadian children <15 years of age.[1] We estimate that approximately 50-60% of children diagnosed with ALL will complete chemotherapy, and consent to participate in the study. We expect to recruit 75–80 children over the enrollment period. To ensure adequate power (>75%) to assess differences in vaccine responses according to treatment protocol, at least 30 subjects will be recruited from centres using DCFI protocols, with the remainder recruited from COG centres. Seventy-five age-matched control subjects will be recruited. If at least 60% of controls have protective antibody titres, a sample of at least 75 cases will give 77% power to detect a  $\geq 20\%$  absolute difference in the proportion of cases achieving seroprotection. This sample size will also give 90% power to detect a standardized difference in mean log titre of  $\geq 0.53$  between cases and controls.

*Safety assessment:* With a total sample size of 75 vaccinees, the probability of detecting at least one occurrence of an AEFI that occurs at a frequency of  $\geq 2\%$  in the population is 0.78 and the probability of detecting an AEFI that occurs at a frequency of  $\geq 1\%$  in the population is 0.53.

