### **6.3 Variables**

#### **6.3.1 Outcomes**

The primary outcomes are the proportion of participants with protective titres ( $\geq 0.35 \mu\text{g/ml}$ ) to the PCV13 serotypes tested, at baseline (compared to age-matched controls), 2 months and 12-15 months post PCV13+PPV23.

Secondary outcomes include baseline GMTs and frequency of protective titres to varicella, pertussis toxin and tetanus among ALL patients versus controls, short-term (baseline to 2 months after vaccination) and long-term (baseline to 12-15 months) vaccine responses to DTaP, based on GMT ratios, the proportion of subjects with protective titres (e.g., tetanus, varicella) and/or the

proportion with an adequate immune response (defined as GMT ratio  $\geq 4$  at 2 and 12-15 months post-vaccination).

**Safety assessment:** The primary outcome is frequency of AEFI of moderate impact or greater (see definitions in section 5.3). The secondary outcomes are frequency of any AEFI and frequency of AEFI deemed to be causally associated with vaccination.

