## **6.4 Statistical Methods**

**Immune responses:** Immune markers (see 5.2) will be compared to age-specific reference values. Baseline GMTs with 95% confidence intervals and proportion with protective titres at baseline will be reported for cases and controls, stratified by interval since last vaccination. Varicella titers will be compared pre-chemotherapy (i.e., at diagnosis) and post-chemotherapy and the proportion with loss of immunity will be reported. The proportion of subjects with GMT ratios  $\geq 4$  or protective titres at 2 and 12-15 months post-vaccination will be reported for pneumococcal vaccines (PCV13+PPV23) and DTaP-IPV-Hib, stratified by age, ALL treatment protocol (COG versus DFCI), interval from last chemotherapy to immunization, and ALL risk category. Vaccine responses will be compared to the expected responses in healthy children based on published clinical trials. Differences among categorical variables will be assessed by Pearson's  $\chi^2$  test or with Fisher exact test when expected cell sizes are  $< 5$ . Independent predictors of low baseline GMTs to tetanus toxoid and pneumococcal serotypes and of an adequate immune response to PCV13+PPV23 vaccination and DTaP-IPV-Hib booster will be assessed using multivariable regression models.

**Safety assessment:** The frequency of low impact, moderate impact and high impact or serious AEFI will be reported by vaccine type, age and ALL risk category, and compared to the published frequencies in healthy children. The frequency of events deemed to be related to vaccination based on the causality algorithm will also be reported.

All statistical analyses will be conducted using SAS® version 9.4 (Cary, NC).

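### The 77% power in Section 6.2 fits 60% versus 80%; with controls at the stated 60% floor and cases 20 points lower, power is about 69–71%

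*Combined protocol and SAP*

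**What the plan says.** Section 6.2 plans 75–80 cases and 75 age-matched controls. For the comparison of proportions it states: "If at least 60% of controls have protective antibody titres, a sample of at least 75 cases will give 77% power to detect a" difference of 20 percentage points or more, described as an "absolute difference in the proportion of cases achieving seroprotection". It does not say which group is expected to be lower, and gives no significance level, sidedness or test.

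Two other power statements stand in the same paragraph:

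- For mean log titres: "This sample size will also give 90% power to detect a standardized difference in mean log titre of" 0.53 or more between cases and controls.
- For treatment protocol: "To ensure adequate power (>75%) to assess differences in vaccine responses according to treatment protocol, at least 30 subjects will be recruited" from DFCI centres, with the remainder from COG centres. No endpoint, response rate or effect size accompanies this claim.

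The direction has to be read from elsewhere. The first objective in Section 2 is "To identify risk factors for low baseline antibody titres to pneumococcal serotypes, tetanus, pertussis toxin, and varicella" in children treated for ALL, compared with controls. Section 1.2 cites studies in which "pneumococcal antibody concentrations were significantly lower in children with ALL who were 3-6 months post-chemotherapy compared to age-matched healthy controls". Section 6.3.1 makes the baseline comparison with controls part of the primary outcome ("The primary outcomes are the proportion of participants with protective titres"). Section 6.4 plans Pearson's chi-square for categorical variables, or Fisher's exact test when expected cells are below 5.

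**The concern.** A condition of the form 60% or more reads as a worst case: whatever the control rate above that floor, the design has at least the stated power. For a fixed 20-point deficit in cases, the opposite is true. The mean of the two proportions is the control rate minus 10 points. At a control rate of 60% that mean is 50%, where binomial variance is greatest and power is lowest. The figure printed beside the floor should therefore be the lowest in the range, but it is the value reached only near 80%.

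What is at stake is how a null result is read. The documents give no pneumococcal seroprotection rate for controls, and several serotypes are compared, so some control rates may fall below 80%. At 60%, the chance of missing a true 20-point deficit is about 30%, not the 23% that the plan implies.

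For DFCI versus COG, a reader cannot tell which difference the minimum of 30 DFCI participants was meant to detect.

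**Working it through.** **Inputs.** From Section 6.2: 75 cases, 75 controls, control rate 60% or more, difference 20 points, stated power 77%. From Section 6.4: Pearson's chi-square. Assumed: two-sided 5%, tested in step 3.

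**Formula (pooled normal approximation, n per group).**
Power = Φ[(|p₁ − p₂| − 1.96·s₀)/s₁], with s₀ = √[2p̄(1 − p̄)/n] and s₁ = √[(p₁(1 − p₁) + p₂(1 − p₂))/n].

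**1. Reproduce the stated 77%: 60% versus 80%.**
- p̄ = 0.70; s₀ = √(2 × 0.70 × 0.30/75) = 0.0748; s₁ = √[(0.24 + 0.16)/75] = 0.0730.
- (0.20 − 1.96 × 0.0748)/0.0730 = 0.730, so power = 76.7%. Exact enumeration of Pearson's test gives 76.8%.
- The stated figure is reproduced for this pair.

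**2. Controls at the 60% floor, cases 20 points lower (40%).**
- p̄ = 0.50; s₀ = √(2 × 0.50 × 0.50/75) = 0.0816; s₁ = √[(0.24 + 0.24)/75] = 0.0800.
- (0.20 − 1.96 × 0.0816)/0.0800 = 0.500, so power = 69.1%.
- Other uncorrected two-sided methods: unpooled normal 70.5%, arcsine 69.4%, exact Pearson 70.6%. Expected cells are 75 × 0.50 = 37.5, so the Fisher fallback does not apply.

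**3. Check the assumed level and sidedness.** Section 6.2 gives 90% power for 0.53 SD. The noncentrality is 0.53 × √(75/2) = 3.246. A two-sided 5% t-test then has 89.7% power and a one-sided test 94.4%. The stated 90% fits two-sided testing.

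**4. Power over the stated range (75 per group, cases 20 points lower, two-sided 5%).**

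| Controls | Cases | Pooled normal | Exact Pearson |
|---|---|---|---|
| 60% | 40% | 69.1% | 70.6% |
| 65% | 45% | 69.6% | 71.5% |
| 70% | 50% | 70.9% | 72.5% |
| 75% | 55% | 73.3% | 73.5% |
| 80% | 60% | 76.7% | 76.8% |
| 85% | 65% | 81.4% | 81.9% |
| 90% | 70% | 87.2% | 88.5% |
| 95% | 75% | 93.7% | 95.5% |

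The pooled figure crosses 77% at a control rate of 80.3%.

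**5. Size of the gap at the floor.** With 80 cases and 75 controls, 60/40 gives 70.5%. Reaching 77% with 60% of controls protected needs a difference of 21.9 points with 75 per group, or about 91 per group for 20 points.

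**6. DFCI versus COG.** With 30 DFCI participants, the remainder is 75 − 30 = 45 to 80 − 30 = 50. With no effect size given, the claimed power cannot be recomputed. It can be turned round, assuming a two-sided 5% level: 75% power needs about 0.63 SD (30 versus 45) or 0.62 SD (30 versus 50). For proportions with 30 versus 45, it needs 30–31 points if the higher rate is 60–70%, 29–30 at 80% and 25–26 at 90%, depending on which group is higher. These differences show what the sample could detect. They do not show that the claim is wrong.

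**The case against.** **The sentence gives no direction.** Read literally, 60% of controls and a 20-point difference allow cases at 80%, and that pair does return 77%. This stands as a reading of the words. It does not rescue the statement, because it puts children recently treated with chemotherapy above healthy controls, against the premise of Sections 1.2 and 2.

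**Control rates may be high.** The only control rates in the documents are the 96–100% in Section 1.2. At rates that high, 77% understates power. Those figures concern other vaccines, such as Hib, hepatitis B, diphtheria and rubella, and the plan itself chose 60% as its condition. It remains true that the shortfall is confined to control rates below about 80% and may not arise for every serotype.

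**A one-sided calculation might lie behind the figure.** One-sided 5% at 60/40 gives 79.4% by the pooled method. One-sided Fisher gives 77.0%, but only with 80 cases; with the 75 stated it gives 72.9%. One-sided testing would also contradict the 90% figure in the same paragraph.

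**Little follows from it.** Enrolment appears to be set by feasibility, and neither 69% nor 77% reaches a conventional 80%. That limits the weight of the point, but a stated power that the design does not have at its own stated condition should still be corrected.

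**The DFCI/COG part is a reporting gap, not an arithmetic error.** That is accepted.

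**Conclusion.** The concern holds. The 77% is correctly computed for 60% versus 80%, but it does not hold for every control rate from 60% upwards when cases are the lower group. At the floor, power is 69.1% (pooled normal) to 70.6% (exact Pearson), a shortfall of about 6 to 8 points. The gap narrows to about 4 points at a control rate of 75% and closes at about 80%; above that the stated figure is conservative.

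This rests on two assumptions that the plan does not state: cases are lower than controls, inferred from its objectives and background, and testing is two-sided at 5%, supported by its own 90% figure for 0.53 SD. The other figures in Section 6.2 that can be checked do reproduce: 90% for 0.53 SD, and the adverse-event detection probabilities, 1 − 0.98⁷⁵ = 0.78 and 1 − 0.99⁷⁵ = 0.53. The mismatch is therefore isolated.

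The DFCI/COG claim of more than 75% power can be neither confirmed nor refuted. It lacks detail and is secondary to the main point.

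**What to change.** Reword Section 6.2 in two places.

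1. **Cases versus controls.** State direction, level and method, and give power by control rate. Suggested text: *With 75 cases and 75 controls (two-sided 5%, normal approximation), power to detect seroprotection 20 percentage points lower in cases is about 69% if 60% of controls are protected, 71% if 70%, 77% if 80% and 87% if 90%.*

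2. **DFCI versus COG.** Give the endpoint, assumed rates and difference behind the claim of more than 75% power. If these cannot be recovered, state what the sample can detect. Suggested text: *With 30 DFCI and 45 COG participants, 75% power (two-sided 5%) requires a difference of about 0.63 SD in mean log titre, or in response rates about 30–31 points if the higher rate is 60–70%, 29–30 at 80% and 25–26 at 90%, depending on which group is higher.*

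The cost is wording only. Design, enrolment, endpoints and analysis stay as they are.

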### **1.5 Rationale**

NACI has identified vaccine safety and effectiveness in immunocompromised individuals as a research priority for vaccines recently introduced in Canada (e.g., PCV13).[36] Among

physicians caring for pediatric ALL patients, there is currently a lack of empirical scientific evidence to guide immunization practices, which has likely contributed to the variation in practices observed in our survey. Although universal PCV immunization programs have been in place for a decade or more in many developed countries, there is a paucity of literature evaluating these vaccines in children with ALL. Infants have been immunized routinely with PCV in Canada since at least 2006, and the 13-valent vaccine has been available since 2010. Most children completing chemotherapy for ALL would have been immunized in infancy with PCV7, but many would never have received a dose of PCV13 or PPV23, which is not routinely administered to healthy children. Due to waning humoral immune responses, children who received PCV13 prior to diagnosis with ALL may also benefit from an additional dose of PCV13, and from PPV23 immunization. It is unclear whether children with ALL are receiving all recommended immunizations and whether they would benefit from additional booster doses of other vaccines such as tetanus-diphtheria-pertussis-containing vaccines (i.e., DTaP) after they complete chemotherapy.

This study will be the first multi-centre study of vaccination in ALL survivors in Canada and among the largest prospective vaccination studies to date in this population. It will provide critical information to identify children with ALL who may be at greater risk for vaccine-preventable infections due to low antibody titres, and will assess immunogenicity and safety of PCV13 and DTaP-IPV-Hib in this population. The study results will support the development of immunization recommendations for children with ALL. This study will also test a methodology to assess vaccine immunogenicity and safety in a high-risk population that, if successful, will be expanded to other groups of immunocompromised children and adults, such as patients who received bone marrow transplants, have primary immunodeficiency or are on high dose steroids.

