### 3.2.2 Controls:

#### *Inclusion criteria*

- Children 3-18 years of age, age-matched to cases
- Caregiver and/or participant is English or French-speaking and able to provide written informed consent

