Blood sampling will be coordinated with routine blood draws, which are conducted at most follow up visits.

Controls:

Past medical history will be reviewed for any excluding conditions and once informed consent has been obtained, immunization records will be obtained as described above. Serum will be collected to measure “baseline” antibody titres to tetanus, PT, varicella, and pneumococcal serotypes, based on the vaccinations received. There will be no further follow-up of controls.

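### The stated 77% and 90% power count all 75 controls, but fewer are likely to be tested for the primary pneumococcal comparison, and section 6.2 makes no allowance for this

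*Combined protocol and SAP*

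**What the plan says.** - **Power (6.2).** "Seventy-five age-matched control subjects will be recruited". The calculation is conditional: "If at least 60% of controls have protective antibody titres", then "a sample of at least 75 cases will give 77% power" to detect a 20-point "absolute difference in the proportion of cases achieving seroprotection". The same sample is said to give 90% power for a standardized difference of 0.53 in mean log titre. Alpha, sidedness and the direction of the 20 points are not stated.
- **Primary outcome (6.3.1).** "The primary outcomes are the proportion of participants with protective titres" (at least 0.35 µg/ml) to the PCV13 serotypes tested. The baseline part is compared with age-matched controls.
- **Control testing (4.2, paragraph on controls).** Serum is used to measure tetanus, pertussis toxin, varicella and "pneumococcal serotypes, based on the vaccinations received".
- **Control eligibility (3.2.2).** "Children 3-18 years of age, age-matched to cases". Neither the inclusion nor the exclusion criteria mention PCV. Section 4.1 puts control recruitment between April 2017 and January 2018.
- **Vaccine dates (1.5).** "Infants have been immunized routinely with PCV in Canada since at least 2006, and the 13-valent vaccine has been available since 2010". The same section adds that many children finishing chemotherapy will never have had a dose of PCV13.

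**The concern.** Controls aged 3-18 and recruited in 2017-18 were born between about 1998 and 2015. Some were born before routine infant PCV and more before PCV13. If a control is tested for pneumococcal serotypes only according to vaccines received, the untested ones have no value to enter in the baseline comparison. The 75 in section 6.2 is the number recruited, not the number with a result for a given serotype.

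What is at stake is how a serotype-level null result is read. A reader who takes 77% as the power of the primary comparison would give a non-significant difference more weight than it may deserve.

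**Working it through.** **Inputs.** From 6.2: 75 cases, 75 controls, 20-point difference, 60% floor for controls, 0.53 SD. Assumed, because not stated: two-sided alpha of 5%, z = 1.96.

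**Formulas.** With n_c controls, n cases, rates p_c and p, and p̄ = (n_c·p_c + n·p)/(n_c + n):

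- Proportions: power = Φ[(|p_c − p| − 1.96·SE0)/SE1], where SE0 = √[p̄(1−p̄)(1/n_c + 1/n)] and SE1 = √[p_c(1−p_c)/n_c + p(1−p)/n].
- Means: power = Φ[0.53·√(n_c·n/(n_c+n)) − 1.96].

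**Step 1: reproduce the plan at 75 v 75.**

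- 60% v 80%: p̄ = 0.70, SE0 = 0.0748, SE1 = 0.0730; (0.20 − 0.1467)/0.0730 = 0.730, so 76.7%. This is the stated 77%.
- 0.53 SD: 0.53 × √37.5 − 1.96 = 1.286, so 90.1%. This is the stated 90%.
- 60% of controls v 40% of cases: p̄ = 0.50, SE0 = 0.0816, SE1 = 0.0800; (0.20 − 0.1600)/0.0800 = 0.50, so 69.1%. The 77% does not hold for this pair.

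**Step 2: how many controls might be tested.** The documents give no control age distribution, PCV coverage or catch-up rate, so every count here is an assumption. Three age models were tried, all with blood drawn April 2017 to January 2018:

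- (a) ages uniform over 3-18;
- (b) ages that follow ALL incidence (section 1.1: 9 per 100,000 at ages 1-4 and about 5 overall, taken as the under-15 average), flat over ages 5-14, plus 2 years of treatment for girls or 3 for boys (1.1.1) and 0.5-1 year after treatment, with 55% boys assumed;
- (c) as (b), with incidence declining over ages 5-14.

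| Born from (assumed cut) | (a) | (b) | (c) |
|---|---|---|---|
| 2002 | 59 | 65 | 70 |
| 2006 | 41 | 50 | 55 |
| 2009 | 27 | 39 | 39 |
| 2010 | 22 | 31 | 31 |

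Entries are controls out of 75. The 2002 row is included because 2006 is only a latest date; 2002 itself is not in the documents. The 2009 row supposes that children born that year received PCV13 at the 12-month dose. The resulting ranges are about 41-70 for any infant PCV and about 22-39 for serotypes added in PCV13.

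**Step 3: power with 75 cases.** Example at 41 controls, 80% v 60%: p̄ = (32.8 + 45)/116 = 0.671, SE0 = 0.0913, SE1 = 0.0843; (0.20 − 0.1789)/0.0843 = 0.250, so 60%.

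| Tested controls | 80% v 60% | 60% v 40% | 0.53 SD |
|---|---|---|---|
| 75 | 77% | 69% | 90% |
| 70 | 75% | 68% | 89% |
| 50 | 66% | 59% | 83% |
| 41 | 60% | 54% | 78% |
| 39 | 58% | 53% | 77% |
| 31 | 51% | 47% | 70% |
| 22 | 39-40% | 38% | 59% |

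(Controls are the first rate in each pair. The 22-control entry for 80% v 60% is 39.5%.)

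**Step 4: if cases fall too.** Objective 1 in section 2 concerns previously immunized cases. As an illustration, if cases fell to the same number as controls, 41 per group would give 51% (80% v 60%) and 67% (0.53 SD), and 22 per group would give 30% and 42%.

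**The case against.** Several points on the other side stand.

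- **The arithmetic in 6.2 is not wrong.** Both figures reproduce. What is missing is an assumption about how many controls are tested.
- **The counts are modelled.** A reader might infer that the documents leave only about 50-65 controls, or 30-35 for serotypes added in PCV13. They do not. At 70 controls power is 75% and 89%, almost the stated values, so for serotypes in any infant PCV the loss could be trivial.
- **2006 is a latest date.** Section 1.5 also says most children completing chemotherapy will have had PCV7 in infancy, and catch-up doses are not addressed. It would go too far to say that most older controls cannot contribute to any PCV serotype.
- **The testing rule is ambiguous.** Section 4.2 does not say whether it works by vaccine or by serotype. If any PCV dose triggers the full panel, the 22-39 range falls away. The phrase could also qualify tetanus, pertussis and varicella, and 6.3.1 does not say that PCV-unvaccinated controls are left out. Nor do the documents list which tested serotypes PCV13 added.
- **The scope is limited.** Only the baseline part of the primary outcome uses controls; vaccine responses are set against published trials. The 90% concerns mean log titre, not the primary proportion. Section 6.4 plans confidence intervals for baseline geometric mean titres and nowhere proposes to read non-significance as similarity.

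None of this supplies the missing allowance. Under every set of assumptions tried, fewer than 75 controls are tested and power is below the stated figure. The ambiguity in 4.2 is itself something the plan has to settle.

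**Conclusion.** The concern holds as a statement about what section 6.2 has secured. The 77% and 90% apply only to antigens for which all 75 controls have a result, and the 77% only to a pair such as 60% v 80%. For the primary baseline comparison of PCV13 serotypes, fewer controls are likely to be tested. With 75 cases, two-sided 5% and the assumed ages and vaccine histories:

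- **Any infant PCV (about 41-70 controls):** about 60-75% for 80% v 60%, 54-68% for 60% v 40%, and 78-89% for 0.53 SD.
- **Serotypes added in PCV13 (about 22-39 controls, only if testing goes by serotype):** about 40-58%, 38-53% and 59-77%.

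Power is lower again if cases are limited to the previously immunized. Separately, at the stated floor, with cases 20 points below 60%, power is 69% even with full testing.

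A reader might infer that the primary comparison has only about an even chance of detecting the planned difference. For 80% v 60%, that depends on by-serotype testing and control counts within the lower range. The documents establish neither.

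**What to change.** 1. **Section 6.2:** limit 77% and 90% to antigens tested in all 75 controls. State alpha, sidedness, the assumed rates in each group and the direction of the 20 points, and include the 60% v 40% case.
2. **Section 4.2:** say whether the control testing rule works by vaccine or by serotype, and which antigens it covers.
3. **Section 6.2, primary pneumococcal comparison:** restate power by serotype group, naming the serotypes in each group, from the expected numbers of tested controls and eligible cases. Show it as a range labelled with its assumptions, not as a single replacement percentage.
4. **During accrual:** update the range from the immunization records that section 4.2 already collects for controls.

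No extra patients are needed. The cost is a short rewrite and less favourable stated power.
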